**Background and Rationale:**

Urinary retention is a common complication following laparoscopic inguinal hernia repair, with recent studies citing the rate of postoperative urinary retention anywhere from 5-11%. Age, history of benign prostatic hypertrophy, general anesthesia, male gender and postoperative narcotic use have been associated with urinary retention following laparoscopic inguinal hernia repair. The exact effects of general anesthesia and a systemic paralytic agent on bladder function and urinary retention are not completely clear. However, it is strongly suggested that the lack of complete bladder musculature recovery and function in the immediate postoperative period and may lead to urinary retention.

Our institutional database contains over 2,500 patients who have undergone either unilateral or bilateral laparoscopic inguinal hernia repair. Currently our overall rate of urinary retention in all patients in our database is 7.3%, or 185 of the 2,551 patients. In the 90 patients who were both over the age of 60 and had benign prostatic hypertrophy symptoms, the rate was 15.6%. Postoperative urinary retention potentially requires prolonged post-anesthesia care unit (PACU) stay, overnight hospital admission, return to the emergency department, need for an indwelling catheter and further physician assessment,

prolonged micturition difficulties, and urinary tract infection and other catheter-related complications.

Urinary retention can be detrimental to the overall health of our surgical patients.

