**Statistical Analysis and Sample Size Justification:**

*Variables/Time Points of Interest* – Basic demographic information for each patient will be obtained from the medical record, such as age, gender, ASA class, and prior medical histories/surgeries. This information will aid in propensity matching for the study. The propensity match will be 1:1 with an equal number of patients in each group. The match will ensure that there is no statistical difference in data points between the groups and it will be performed by our statistician using SAS. The primary outcome variable, postoperative urinary retention, is a categorical variable (yes/no) that will be documented in postoperative recovery after the patient's operation. Length of stay and hospital cost, continuous variables, will be recorded at the completion of the patient's hospital stay. Information about quality of life will be obtained postoperatively in clinic. The demographic information, primary and secondary outcomes will be entered into our institutional database along with the other information that is typically recorded, such as operative characteristics and patient follow up.

*Statistical Methods* - Data will be analyzed using Statistical Analysis Software, version 9.4 (SAS Institute, Inc., Cary, NC); this task will be performed by the statistician employed by our division. Descriptive statistics will be reported as means with corresponding standard deviations for continuous variables and percentages for categorical variables. Continuous and ordinal variables will be evaluated with the Wilcoxon-Mann Whitney and the Kruskal-Wallis tests. The Wilcoxon-Mann Whitney test will be used when normality exists and there are two variables for comparison, otherwise, the Kruskal-Wallis test will be used. For categorical variables, a Pearson chi-square will be used, and a Fisher exact test will be utilized with a small sample size (i.e. less than five). A two-sided p-value of <0.05 will be used for all significance determinations.

*Power/Sample Size* – Using SAS, the power for our study was calculated using the postoperative urinary retention rate at our institution, 7%, compared to a current 0.5% postoperative urinary retention rate using Sugammadex. With 80% power, we would need to enroll 140 patients per group. The data for this project will be interpreted by the PI for the project as well as the co-investigators.

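### Does the undefined chi-square/Fisher switch, with no statement on pairing, leave the primary test open in a way that matters?

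*Combined protocol and SAP*

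**What the plan says.** All the relevant text is in the protocol's section on statistical analysis and sample size justification. The primary outcome, "postoperative urinary retention, is a categorical variable (yes/no"), has no test of its own. One general rule covers every categorical variable: "a Pearson chi-square will be used, and a Fisher exact test will be utilized with a small sample size (i.e. less than five"). The same section says of the groups: "The propensity match will be 1:1 with an equal number of patients in each group". Study Design/Methods lists the matching factors, but neither section mentions a paired analysis, and every test named is for independent samples.

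The power paragraph takes "the postoperative urinary retention rate at our institution, 7" percent, "compared to a current 0.5% postoperative urinary retention rate using Sugammadex", and concludes: "With 80% power, we would need to enroll 140 patients per group". It does not name the test that was powered. For continuous and ordinal variables the plan states: "The Wilcoxon-Mann Whitney test will be used when normality exists" and two variables are compared; otherwise Kruskal-Wallis applies.

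**The concern.** The threshold can be read in three ways: the smallest expected cell count (the textbook convention), the smallest observed cell count, or literally the number of patients. The design's own rates put the expected retention count only just above five, so the readings send the primary comparison to different tests. Near the 5% limit the two tests can disagree. With 2 against 9 events, chi-square gives p = 0.031 and Fisher p = 0.060. If the reading were picked once the counts were known, the primary conclusion could turn on that choice.

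The pairing gap adds a second open choice, because matched groups may be analysed either with or without regard to the pairs.

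**Working it through.** **Inputs** (statistics section): control rate 7%, Sugammadex rate 0.5%, n = 140 per group, two-sided 0.05. Results come from full enumeration of two independent binomials, unless stated otherwise.

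**Stated sample size.** Fisher's exact test has power 79.9% at n = 139 and 80.3% at n = 140. So 140 is the smallest n that reaches 80% with Fisher. That Fisher was the powered test is an inference, but the figure stands.

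**Where the threshold falls.** Expected events are 140 × 0.07 + 140 × 0.005 = 9.8 + 0.7 = 10.5. With equal groups and t events in total, the expected retention count is t/2 per group, here 5.25. It is below five when t ≤ 9. This trigger depends only on the total, so it favours neither group.

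| Reading of the rule | Fisher used in | Power, 7% vs 0.5% | Type I error, 7% in both |
|---|---|---|---|
| Number of patients (literal) | never | 88.8% | 4.65% |
| Smallest expected count | 39.1% of trials | 82.6% | 4.6% |
| Smallest observed count | 99.9% of trials | 80.3% | 3.9% |
| Fisher always | all trials | 80.3% | 2.7% |

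**How often the conclusion differs.** Chi-square is significant and Fisher is not in 8.5% of trials; the reverse does not occur. Of this, 6.2 points separate the literal reading from the expected-count reading, and 2.3 points separate the expected-count and observed-count readings (82.6% − 80.3%).

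**Two examples.** With equal groups, chi-square = 2n(a − b)² / [t(2n − t)].
- 1 vs 7: 280 × 36 / (8 × 272) = 4.63, p = 0.031; Fisher p = 0.066. Here t = 8, so both count readings select Fisher. Only the literal reading gives a significant result.
- 2 vs 9: 280 × 49 / (11 × 269) = 4.64, p = 0.031; Fisher p = 0.060. Here t = 11, so the two count readings do part.

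**Type I error if the choice were made afterwards.** Always taking the smaller of the two p-values has a maximum size of 5.0% over common rates from 0.5% to 13.5%, the same as chi-square alone. Freedom between the two listed tests therefore cannot push the error above the nominal level in that range.

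**Pairing.** Like should be compared with like. With uncorrelated pairs, exact McNemar has 80.7% power against 80.3% for Fisher. McNemar mid-p has 87.9% against 88.8% for unpaired chi-square. The apparent gain of mid-p over Fisher comes from the mid-p device, not from pairing.

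The documents give one handle on the within-pair correlation. Background and Rationale reports 185 of 2,551 patients with retention (7.25%), and 15.6% (14 of 90) among those over 60 with BPH symptoms. That leaves 171 of 2,461 = 6.95% in the rest. With w = 90/2,551 = 0.0353, perfect matching on this factor alone gives a correlation of

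w(1 − w)(0.1556 − 0.0695)² / [0.0725 × 0.9275] = 0.0340 × 0.00741 / 0.0673 ≈ 0.004.

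Other matching factors could add to this, but the documents give no figures for them.

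**The Wilcoxon sentence.** The Wilcoxon-Mann-Whitney test needs no normality, and for two groups Kruskal-Wallis is the same test apart from any continuity correction. The slip is clerical and changes no two-group result.

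**The case for a change.** The case for a change rests on more than the design point. Background and Rationale describes "recent studies citing the rate of postoperative urinary retention anywhere from 5-11" percent. At a 5% control rate chi-square and Fisher disagree in 17.7% of trials. If the Sugammadex rate is 2% instead of 0.5%, the two count readings themselves differ in 10.1%. The study is open-label, its comparator is retrospective, and the division's own statistician both matches and analyses. Fixing the test in advance costs one sentence and is one of few safeguards available.

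Part of this stands. The definition is missing, and naming the test before outcomes are analysed would be good practice. The rest carries less weight:

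- Of the 17.7%, 16.1 points need the literal reading, which would make the Fisher clause pointless for a comparison of 280 patients. The count readings differ in 1.6% there, and in 0.6% at an 11% control rate.
- The 10.1% is real. It arises where the drug works much less well than assumed and power is about 51% or 41% under the two count readings. The effect assumption drives that shortfall far more than the switch does.
- Ignoring positively correlated pairs makes the unpaired tests conservative. With an assumed correlation of 0.2 at a 3.5% rate in both groups, chi-square's size falls from 4.45% to 2.6%. That would not be trivial, and exact McNemar would then reach 87.7% power at the design rates. But 0.2 is far above the 0.004 that the documents' own subgroup figures suggest.
- Practice on pairing after propensity matching varies. A plan that lists only unpaired tests is most naturally read as choosing an unpaired analysis.

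**Conclusion.** The observation is accurate, but no change follows. The plan leaves three things unwritten: what is compared with five, the named test for the primary outcome, and the treatment of pairs. A competent analyst would take the expected-count convention and the unpaired tests listed. That gives 82.6% power at the design rates; the strictest unpaired reading gives 80.3%, still at the stated 80%. Type I error stays within 5.0%, the 140 per group reproduces, and the two sensible readings part in 2.3% of trials. Moving to a paired test would be a reasonable alternative with little demonstrated gain.

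This rests on the design rates, on independent groups, and on common rates between 0.5% and 13.5% for the error bound. It also assumes that the analyst stays with the listed unpaired tests: the bound does not cover a later choice between paired and unpaired methods.

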### **Risks and Benefits**

The risk to the patient is minimal. Common side effects of Sugammadex are dizziness, tremor, lightheadedness, hypotension and tachycardia, but they are rare. Patients will be excluded with renal disease or neuromuscular disease, which could be exacerbated by the use of Sugammadex. Women of childbearing age will be encouraged to use a second form of barrier contraceptive to prevent pregnancy. Adverse Experience Reporting will proceed in accordance with the policies and standards of Atrium Health. Patients in the study will be informed to report any adverse experiences related to this study directly to the research staff for the division. Reporting of such events can also be made directly to North Carolina Department of Health and Human Services.

Based on the limited amount of patients who have received Sugammadex to this point at CMC, we anticipate decreased rates of postoperative urinary retention. A decrease in urinary retention would be the main benefit for patients.

### **Confidentiality and Data Storage**

Data will be collected electronically for this project and be stored on a secure server that is accessible only by password to the research team. Information for the study will be de-identified and names and medical record numbers will not be used in presentation or publication of the data. The data itself will be kept for a period of 5 years after study closure and destroyed by overwriting and deleting the file

### **Data and Safety Monitoring**

The principal investigator will be responsible for the overall monitoring of the data and safety of study participants. The principal investigator will be assisted by other members of the study staff. [name] ([contact]) will serve as the DSMP for this study.

### **Reporting of Unanticipated Problems, Adverse Events or Deviations**

Any unanticipated problems, serious and unexpected adverse events, deviations or protocol changes will be promptly reported by the principal investigator or designated member of the research team to the IRB and sponsor or appropriate government agency if appropriate.

